10.2. PROTOCOL DEVIATIONS

All deviations from the protocol will be reviewed and classified as major or minor prior to the database freeze for the final analysis of the Main study period. The full list of possible protocol deviations will be included in the study protocol deviation log which will include the classification (major or minor). The excel protocol deviation log will then be imported in SDTM.

Major protocol deviations will be summarized by deviation term in the ITT/Safety analysis set. A by-subject listing of all protocol deviations (major and minor) will be presented and will include the type of deviation and description.

11. DEMOGRAPHIC AND OTHER BASELINE CHARACTERISTICS

Demographic data and other baseline characteristics will be presented for each analysis set (except the SCR analysis set) described in section 5 of this analysis plan.

No statistical testing will be carried out for demographic or other baseline characteristics.

The following demographic and other baseline characteristics will be reported for this study:

- Age (years)
- Sex
- Race
- Ethnicity
- Weight (kg)
- Height (cm)
- Body mass index (BMI) (kg/m²)
- Alcohol/Tobacco consumption
- ECOG-PS

A by-subject listing showing the demographic characteristics will be provided.

The baseline disease characteristics to be summarized will include:

- Stage at initial diagnosis
- Site of primary tumour
- Histological diagnosis
- Whether the current stage of disease is metastatic or not
- Locally advanced/unresectable disease

Document: T:\sas\Debiopharm\Debio_1143\CZA60507\Biostatistics\Documentation\SAP\SAP Text\V5

Author: XXXXXXXXXX Version Number: 5.0
Version Date: 19APR2022

Template No.: CS_TP_BS016 Revision 5
Effective Date: 01Apr2018

Reference: CS_WI_BS005

- Tumor Nodes Metastasis (TNM) classification at initial diagnosis (only for cohort 2)
- Time since initial diagnosis (months)
- Prior known PD-L1 expression status
- Molecular phenotype information (only for cohort 3 & 4)

All disease characteristics at baseline will also be listed.

11.1. DERIVATIONS

- $BMI (kg/m^2) = \text{weight (kg)} / \{\text{height (m)}\}^2$
- $\text{Time since initial diagnosis (months)} = (\text{treatment start date} - \text{initial diagnosis date}) / 30.4375$

12. MEDICAL HISTORY

Medical history information will be presented for the SAF analysis set.

Medical history will be coded using the latest version of the Medical Dictionary for Regulatory Activities (MedDRA) available at the time of the analysis.

Medical history are reported in "General Medical History" CRF page.

Medical history will be summarized by the number and proportion of subjects within each preferred term (PT), and system organ class (SOC).

Medical history will also be provided in a data-listing including the information on: SOC, PT, reported term, start and end date.

13. PRIOR ANTI-CANCER TREATMENTS

Prior anti-cancer treatments will be presented for the SAF analysis set.

Tabulations for prior anti-cancer treatments will include:

- Prior treatment with radiotherapy
 - Radiotherapy site or region
 - Reason for radiotherapy
- Prior treatment with systemic therapy
 - Intent of therapy

Document: T:\sas\Debiopharm\Debio_1143\CZA60507\Biostatistics\Documentation\SAP\SAP Text\V5

Author: XXXXXXXXXX Version Number: 5.0
Version Date: 19APR2022

Template No.: CS_TP_BS016 Revision 5
Effective Date: 01Apr2018

Reference: CS_WI_BS005

Copyright © 2009, 2010, 2012, 2016, 2018 IQVIA. All rights reserved. The contents of this document are confidential and proprietary to IQVIA Holdings Inc. and its subsidiaries. Unauthorized use, disclosure or reproduction is strictly prohibited.

- Therapy class/ Cancer therapy agent
- Best overall response achieved over all and for each prior therapies
- Reason for therapy discontinuation
- Prior anti-cancer surgery
 - Name of surgery
 - Location
 - Received surgery with curative intent? Best outcome achieved over all surgeries, presented separately for metastatic and locally advanced/unresectable patients as recorded on the cancer diagnosis eCRF

Additionally, prior anti-cancer therapies will be listed and will include:

- Prior radiotherapy: site or region, start/end date, total dose, dose per fraction, reason
- Prior systemic therapy: line of therapy, intent of therapy, cancer therapy agent (coded in WHODrug), therapy class, start/end date, reason for therapy discontinuation, date of progression (if applicable), best overall response
- Prior cancer surgery: name, location, date, whether the surgery was curative in intent, outcome

Additionally, prior and current anti-cancer treatments will be listed and will include:

- Prior systemic therapy: line of therapy, therapy class, cancer therapy agent (coded in WHODrug), start/end date, reason for therapy discontinuation, date of progression (if applicable), best overall response
- Study drug exposure (Debio 1143): primary tumor location, start/end date, time to progression or death, confirmed best overall response, ongoing on treatment
- Molecular phenotype: prior PDL-1 expression, applicable only to Cohort 3 and 4

14. MEDICATIONS

Medication information will be presented for the SAF analysis set.

Medications will be coded using the latest version of the WHODrug dictionary available at the time of the analysis.

See section 8.2.2 for handling of partial dates for medications, in the case where it is not possible to define a medication as prior, concomitant, or post treatment, the medication will be classified by the worst case; i.e. concomitant.

Document:	T:\sas\Debiopharm\Debio_1143\CZA60507\Biostatistics\Documentation\SAP\SAP Text\V5	Version Number:	5.0
Author:	██████████	Version Date:	19APR2022

Template No.: CS_TP_BS016 Revision 5
 Effective Date: 01Apr2018

Reference: CS_WI_BS005

Pre-medications are medications which started and stopped prior to the first dose of any study medication.

Concomitant medications are medications which:

- started prior to, on or after the first dose of any study medication but no later than the last administration of any study drug
- AND ended on or after the date of first dose of any study medication or were ongoing at the end of the study.

Post-medications are medications which started after the last dose of any study drug .

Pre- and concomitant medications will be summarized by anatomical therapeutic chemical (ATC) levels 2 and 4.

All medications and procedures date will also be listed.

15. STUDY MEDICATION EXPOSURE

Exposure to any study medication, in weeks, will be presented for the RP2D (Part A only), SAF and EFF (Part B only) analysis sets.

The date of first study medication administration will be taken from the eCRF study drug exposure forms. The date of last study medication will be taken from the eCRF End of Treatment form.

The following information will be summarized in tables:

- Duration of exposure (weeks)
- Cumulative dose (mg), for cycle 1 and overall
- Number of administrations of Debio 1143, for cycle 1 and overall
- Number of infusions for Nivolumab (cycle 1 and full treatment period)
- Number of cycles for Nivolumab
- Details on treatment modifications
 - Number of patients having at least one Debio 1143 interruption, for cycle 1 and overall
 - Number of patients having at least one dose reduction (as defined in protocol section 5.4)
 - Summary of the number of interruptions of Debio 1143, for cycle 1 and overall
 - Summary of the number of patients having at least one interruption in the following durations (< 3 days, >= 3 days, >= 6 days, >= 14 days), for cycle 1 and overall
 - Summary of the cumulative duration of Debio 1143 interruption, for cycle 1 and overall
 - Incidence of action taken with Debio 1143/nivolumab and main reason for action taken

All exposure data as recorded exposure in the study drug exposure forms will be included in a listing. Also, data

Document: T:\sas\Debiopharm\Debio_1143\CZA60507\Biostatistics\Documentation\SAP\SAP Text\V5

Author: [REDACTED] Version Number: 5.0
Version Date: 19APR2022

Template No.: CS_TP_BS016 Revision 5
Effective Date: 01Apr2018

Reference: CS_WI_BS005

Copyright © 2009, 2010, 2012, 2016, 2018 IQVIA. All rights reserved. The contents of this document are confidential and proprietary to IQVIA Holdings Inc. and its subsidiaries. Unauthorized use, disclosure or reproduction is strictly prohibited.

recorded in the Debio 1143 and nivolumab accountability eCRFs will be listed.

15.1. DERIVATIONS

- Duration of exposure (weeks)
 - Debio 1143: $(\text{date of last dose of Debio 1143} - \text{date of first dose of Debio 1143} + 1) / 7$
 - Nivolumab: $(\text{date of last dose of nivolumab} - \text{date of first dose of nivolumab} + 1) / 7$
- Actual Cumulative dose
 - Debio 1143 (mg): sum of the actual administered dose across all dosing dates
 - Nivolumab (mg): sum of the total dose administered across all cycles, if an infusion was interrupted then the total volume infused will be used to calculate the effective mg quantity administered ($\text{planned dose} \times (\text{total volume infused} / \text{total volume prepared})$)
- For every unique interruption, defined as any occurrence of a 0 mg dose succeeding a non-0 mg dose, the duration of unique Debio 1143 interruption = $(\text{date of last day with Debio 1143 exposure form completed with actual dose of 0 mg} - \text{date of first day with Debio 1143 exposure form completed with actual dose of 0 mg}) + 1$

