## 5.3. Study treatments

### Debio 1143: rationale for dose regimen

Since Debio 1143 is a chemosensitizer, radiosensitizer and immunosensitizer, its schedule of administration in clinical trials is adapted to the standard treatment used in the combination.

A 10-day on / 4-days off schedule given every 2 weeks (i.e., repeated twice in a 4-week cycle) of Debio 1143 was selected to optimize the activity of the combination with standard nivolumab. This schedule is being tested in an ongoing Debio 1143-NSCLC-105 study in combination with avelumab (NCT03270176). The 4-day wash-out period allows recovery from potential Debio 1143-related toxicity and gives a lower

cumulative dose per cycle than regimens using 14 days q3w (14 days on and 7 days off) while providing similar dose-density and intensity. As of 31 July 2018 (IDB cut-off), up to 13 patients had been treated in the Debio 1143-NSCLC-105 study: all 4 planned dose levels (150 to 250 mg/d) had been explored without reaching a formal MTD. No unexpected toxicities were observed and the 200 mg/d dose is currently being expanded formally.

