Treatment must be re-started with a Debio 1143 dose reduction. Individual patients may have up to two dose adjustments of 50 mg/d (each one) up to a minimum dose of 100 mg/d Debio 1143 (i.e. 1st dose reduction 150 mg/d, 2nd dose reduction 100 mg/day). Patients still requiring a dose adjustment with a dose of 100 mg/d will be withdrawn from the study. Once adjusted, Debio 1143 dose will not be re-escalated under any circumstances.

Up to 2 dose reductions must be implemented in the event of any of the following:

- Any Debio 1143-related Grade 4 hematologic toxicity
- Debio 1143-related febrile neutropenia any grade, or Grade 3 thrombocytopenia if associated with bleeding or requiring platelet transfusion
- Debio 1143-related grade 2 or higher alanine transaminase (ALT)/ aspartate transaminase (AST) increase with a concurrent increase of total bilirubin  $\geq 2$  x upper limit of normal (ULN) and concurrent with alkaline phosphatase (ALP)  $\leq 2$  x ULN (Hy's law), in the absence of objective causes of biliary obstruction due to obvious disease-related causes
- Any Grade 3, treatment-related, non-hematologic clinical toxicity lasting 3 or more days despite optimal supportive care, or requiring admission for appropriate medical management; hypersensitivity and/or infusion-related reactions are excluded if not reoccurring after appropriate pre-medication and/or prolonging infusion time
- Grade 3 non-hematologic laboratory value (excluding lipase, amylase and/or autoimmune endocrinopathies manageable by replacement therapies)
- A delay of  $>2$  weeks due to drug-related toxicity in initiating subsequent cycles, or a second delay lasting  $>24$  h but  $<2$  weeks
- Unable to complete at least 70% of the scheduled treatment, i.e. more than six Debio 1143 skipped doses during any cycle due to treatment-related toxicity or more than 2 treatment interruptions  $>24$  h but  $<6$  days

If for any reason Debio 1143 is withheld temporarily, nivolumab will also be withheld until treatment may be resumed. Patients discontinuing Debio 1143 definitively for any reason will also discontinue nivolumab study treatment.

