## **7.6. Method of administration and compliance**

### **7.6.1. Debio 1143**

Debio 1143 capsules are ready to use and will be taken orally once daily for 10 consecutive days every 2 weeks of a 28-day cycle (Days 1 to 10 and Days 15 to 24 q4w).

Patients should fast 2 hours before dosing and should fast at least 1 hour post-dose. Water is permitted freely. Beyond the onsite visits, study medication will be self-administered by patients at home and should be taken at approximately the same time each day. If a dose is forgotten, the patient may take the dose later in the day but no later than 6 h after normal intake time. If the delay exceeds 6 h, the patient must wait until the next scheduled administration. A double dose should not be taken to make up for a missed dose.

If a patient vomits after study medication intake, the patient should not take another dose, but wait until the next scheduled dose. If vomiting persists, the patient should contact the Investigator. Relevant medical instructions should be given to the patient, specifically to not replace any missing doses and to not extend treatment beyond Days 10 or 24, during each cycle for any reason. In addition, the patient should be instructed to record any occurrences of vomiting in the diary card.

Patients' compliance will be verified on Day 1 of each cycle and on days when PK sampling is scheduled during Cycles 1 and 3, if applicable. Compliance will be measured by direct visual supervision at dosing by the Investigator or his/her designee when administered at the hospital, or by means of a diary card to be filled out after each dose when taken at home (the number of capsules, date and time of dosing will be recorded). The diary card will be checked by the Investigator or his/her designee at each study visit. Any change in the daily dosing of Debio 1143, must be appropriately reflected in the patient's diary by the Investigator or his/her designee, such as dose reduction, dose omissions, and treatment resumption, as applicable.

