16.1. DERIVATIONS

- Treatment compliance (%) = $(\text{actual cumulative dose} / \text{planned cumulative dose}) * 100$

Planned dose by cycle:

- Debio 1143 (mg): $20 * 200 = 4000$
- Nivolumab (mg): 480

Planned cumulative dose:

Document: T:\sas\Debiopharm\Debio_1143\CZA60507\Biostatistics\Documentation\SAP\SAP Text\V5

Author: XXXXXXXXXX Version Number: 5.0
 Version Date: 19APR2022

Template No.: CS_TP_BS016 Revision 5
 Effective Date: 01Apr2018

Reference: CS_WI_BS005

Copyright © 2009, 2010, 2012, 2016, 2018 IQVIA. All rights reserved. The contents of this document are confidential and proprietary to IQVIA Holdings Inc. and its subsidiaries. Unauthorized use, disclosure or reproduction is strictly prohibited.

- Debio 1143 (mg): Number of cycles started x Planned dose by cycle
- Nivolumab (mg): Number of cycles started x Planned dose by cycle

When Debio 1143 is ongoing, cycle starts if at least one dose of Debio 1143 > 0 is received on Day 1. Cycle period is defined from Day 1 of current cycle to day before Day 1 of the next cycle.

If Debio 1143 stopped but Nivolumab is ongoing, cycle period is defined as 28 days, continuing from the date of last Debio 1143 administration >0. (ie. For example, if last Debio 1143 administration is on 1APR21 corresponding to C4D17, next Nivolumab administration received on 14APR21 would correspond to C5D2).

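### The SAP's Debio 1143 interruption length does not remove planned rest days, so the same number of missed doses can fall in different duration classes

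*SAP*

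**What the plan says.** SAP 15.1 derives a duration "For every unique interruption, defined as any occurrence of a 0 mg dose succeeding a non-0 mg dose". The duration is the "date of last day with Debio 1143 exposure form completed with actual dose of 0 mg" minus the "date of first day with Debio 1143 exposure form completed with actual dose of 0 mg", plus one. SAP 15 uses it for a "Summary of the number of patients having at least one interruption in the following durations", namely under 3, at least 3, at least 6 and at least 14 days. It also uses it for cumulative interruption time. Both are shown for cycle 1 and overall, alongside the number of interruptions and the number of patients with at least one.

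Protocol 7.6.1 gives the dosing days as "Days 1 to 10 and Days 15 to 24 q4w", and Protocol 5.3 describes "A 10-day on / 4-days off schedule given every 2 weeks". Days 11 to 14 and 25 to 28 are therefore planned rests. Neither SAP 15 nor SAP 15.1 mentions them. The documents do not say whether an exposure form is completed on a rest day, or whether a run of 0 mg records is split at a rest.

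**The concern.** The rule works on form dates, while the drug is scheduled in two 10-day blocks separated by 4-day gaps. When 0 mg records fall on both sides of a gap, the gap is added to the length. Two patients who missed the same number of doses can then land in different classes only because of where in the cycle the misses fell. A reader of the exposure tables would take the at-least-6-day and at-least-14-day rows as a measure of lost treatment, and they would not be one. If rest days carry 0 mg forms, the counts of interruptions and of affected patients would be inflated as well.

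**Working it through.** **Inputs.** Dosing days are Days 1 to 10 and 15 to 24 (Protocol 7.6.1). The duration formula is from SAP 15.1 and the classes are from SAP 15. The documents state no interruption duration to reproduce. As a check on the calendar, the schedule has 20 dosing days per cycle. 20 × 200 mg = 4000 mg, the planned dose per cycle in SAP 16.1. 30% of 20 = 6, the maximum of missed doses in the 70% rule of SAP 6.2.

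**Formula.** Length = last 0 mg form date − first 0 mg form date + 1. A run ends at the next non-zero record.

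**Two readings.** Reading A: forms exist only for scheduled dosing days. Reading B: rest days also carry a 0 mg form.

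| Days missed | Scheduled doses missed | Length, reading A | Length, reading B |
|---|---|---|---|
| none | 0 | no interruption | 4 (Days 11–14) and 4 (Days 25–28) |
| 10 | 1 | 1 | 14 − 10 + 1 = 5 |
| 9, 10 | 2 | 10 − 9 + 1 = 2 | 14 − 9 + 1 = 6 |
| 10, 15 | 2 | 15 − 10 + 1 = 6 | 6 |
| 15, 16 | 2 | 16 − 15 + 1 = 2 | 16 − 11 + 1 = 6 |
| 9, 10, 15 | 3 | 15 − 9 + 1 = 7 | 7 |

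Under reading B the rows with misses also show the 4-day rest on Days 25–28 as a further interruption.

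**Comparison of the three two-dose cases.** By doses not taken, all three are 2. By days between the last dose taken and the next, all three are 6 (Days 9–14, 10–15 and 11–16). Reading A gives 2, 6 and 2, which matches neither measure. It puts one case in the at-least-6-day class and two in the under-3-day class. Reading B gives 6, 6 and 6, but it also gives a fully compliant cycle two interruptions totalling 4 + 4 = 8 days.

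**A case that follows the protocol's resumption rule.** Under Protocol 5.4, a mid-cycle interruption that does not recover within 72 hours resumes on Day 1 of the next cycle. Suppose 0 mg forms are completed on dosing days through Day 24 (reading A). An interruption starting on Day 10 then scores 24 − 10 + 1 = 15 days for 1 + 10 = 11 doses. One starting on Day 15 scores 24 − 15 + 1 = 10 days for 10 doses. One extra dose adds five days and moves the patient into the at-least-14-day class.

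**The case against.** The best defence is that calendar time was intended. Protocol 5.4 has day-based limits as well as dose counts: up to 3 consecutive days, interruptions shorter than 6 days, and delays of more than 2 weeks. The SAP classes of 3, 6 and 14 days resemble these, and a single 10-day block cannot reach 14 days. Calendar days off drug is a legitimate exposure measure. So it would be wrong to say that the protocol counts only skipped doses.

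That part stands, but it does not rescue the formula. With dosing-day forms, a patient who missed Days 9 and 10 was off drug for 6 days and is reported at 2. With rest-day forms, planned rests are reported as interruptions. A 14-unit class does not show that elapsed time was meant either: Days 7 to 10 plus 15 to 24 make 4 + 10 = 14 scheduled doses.

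A second defence is that missing exactly Days 10 and 15 is narrow, because the Day 15 dose is given on site. That is fair as to frequency. But Day 10 can be forgotten at home and Day 15 omitted under the re-treatment criteria. The formula then also merges two separate one-dose misses into one interruption. The 72-hour resumption rule produces longer spans across the rest without any protocol deviation.

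**Conclusion.** The concern holds as a minor defect in the derivation of descriptive tables. Under either reading the rule misclassifies. With dosing-day forms, two missed doses score 2 or 6 days depending on position, and two is the smallest number of missed doses that can reach the at-least-6-day class. With rest-day forms, a compliant cycle shows two 4-day interruptions. The tables affected are the duration classes and cumulative duration and, only if rest days carry forms, the interruption and patient counts.

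Three stronger inferences are not supported:

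- **Every planned rest is counted.** This needs 0 mg forms on rest days, and no text says they exist. Protocol 7.6.1 has the diary filled in after each dose, which makes it less likely. Otherwise a rest counts only when 0 mg records lie on both sides of it.
- **The RP2D decision, compliance or a formal endpoint is distorted.** Dose escalation uses DLTs and patient profiles built on raw data (SAP 5.1). DLT evaluability counts missed doses (SAP 6.2), and compliance is in mg (SAP 16.1). The secondary endpoint is the incidence of discontinuations and modifications due to adverse events (SAP 3.2); adverse events leading to interruption are taken from the action-taken field of the adverse event form (SAP 18.1.8). The primary endpoint does not use exposure duration.
- **A gap running into the next cycle contains missed Day 1 and Day 2 doses.** Under Protocol 5.4 and SAP 16.1 a cycle starts with a Debio 1143 dose on Day 1. An undosed Day 1 is a cycle delay, not a skipped dose.

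How many patients would change class cannot be estimated from the documents.

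**What to change.** In SAP 15.1, identify interruptions from scheduled dosing days only (Days 1 to 10 and 15 to 24), so that a rest day can never start or lengthen one. Report interruption length and cumulative duration as scheduled doses not taken. The three two-dose examples then all score 2. State whether rest days carry exposure forms, and whether misses on both sides of a rest form one interruption or two.

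If the 3, 6 and 14-day classes are meant as elapsed time, keep them for a separately labelled measure of calendar days off drug, with its start and end defined. Relabelling the classes as dose counts would change their meaning: 14 consecutive scheduled doses span at least 18 calendar days (for example Days 7 to 24).

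If the protocol's rule on "more than six Debio 1143 skipped doses during any cycle" is to be shown, tabulate total skipped doses per cycle, because that rule is a total and not a consecutive run.

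The cost is SAP wording and a small programming change; no new data are needed.
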